http://www.contecmed.com/index.php?page=shop.product_details&flypage=flypage.tpl&product_id=118&category_id=27&option=com_virtuemart&Itemid=618

Heartbeat's intent is that the current blood pressure reading would then be made available to both the client and the health provider through separate web-based interfaces. Providers would be able to log onto the HeartBeat web-based application from anywhere to review and monitor the blood pressure of multiple clients, while clients can log onto the application to track their own measurements.

2. Study purpose

Though the Contec finger pulse oximeter has been approved for use by Health Canada (Licence No. 90629) and the FDA (<https://www.accessdata.fda.gov/scripts/cdrh/cfdocs/cfRL/rl.cfm?lid=465210&lpcd=DQA>), the proprietary algorithm developed by Heartbeat Technologies Ltd. has not been approved for use. The purpose of this study is to validate the accuracy of the algorithm as compared with the standard manual sphygmomanometer with stethoscope for measuring blood pressure. If the algorithm is shown to be accurate, Heartbeat Technologies Ltd. will apply to Health Canada and the FDA for approval for its use to measure blood pressure.

3. Study Design/Methodology

Trial registration

This study will be registered with ClinicalTrials.gov as it is one of two registered bodies approved and recommended by Health Canada. This will serve as a publicly accessible platform for patients and practitioners to understand the current study's objectives and goals, and be kept informed of the results.

Protocol

The European Society of Hypertension International Protocol revision 2010 for the validation of blood pressure measuring devices in adults (ESH-IP) (**Appendix A**) (O'Brien et al., 2010) will be followed precisely, except it will be modified to follow the extra guidance in the international consensus statement for validation (**Appendix B**) (Stergiou et al., 2018). The international consensus statement (Stergiou et al., 2018) reviewed the adequacy of the number of participants in a variety of established protocols including the ESH-IP, and recommended that, to increase study power and accuracy, the number of participants in a study following the ESH-IP should be at least 85 rather than 33 as in the 2010 version of the ESH-IP.

Setting and clinicians

Study site

The study site will be a room with a comfortable temperature and with no noise or other influences that may cause disturbance, such as telephones.

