Health professionals involved

A supervisor and two observers are required to take the necessary recordings for this study. Three registered nurses will be identified for the study, with training and experience in blood pressure measurement. One will act as the supervisor and two will act as the observers, as specified in ESH-IP. These roles will be outlined below in the section entitled "Interactions with participants and data collection".

Clinicians who participate in this study will be trained and experienced in blood pressure measurement. They will be instructed to follow the ESH-IP guidelines for data collection and record all blood pressure measurements to the nearest 2 mmHg.

A familiarization session with the supervisor and the observers will be held in advance of interactions with participants. This session will involve a number of test measurements. The agenda for the session with the supervisor, who will be recording the data from the observers and from the novel approach, can be seen in **Appendix C**.

Conventional equipment

Two standard mercury sphygmomanometers, the components of which will be checked carefully before the study, will be used as the reference standards by the observers. They will be within 1m of where the observers will be when interacting with a participant, so that they will be able to follow the menisci at eye level from 40mmHg to 180 mmHg. Bladders of multiple sizes will be made available so that, on each subject, there is one of sufficient length to encircle 80%–100% of the arm circumference. The observers will be supplied with good quality non-electronic stethoscopes with well-fitting earpieces.

Heartbeat equipment

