The pulse oximeter, the Heartbeat application (MediBeat), and the supervisor's smartphone (Samsung Galaxy Xcover 4 with Bluetooth connectivity) will be charged, and tested each day of interactions with participants. Prior to conducting the study session, the equipment will have to be calibrated for each participant. The first step of the calibration process is to manually enter the reference data (date of birth, height, weight, baseline manual blood pressure reading and heart rate). Once data is entered, and participant has been given 10 minutes of rest, the nurse supervisor will ensure the participant is seated comfortably, with their legs uncrossed, back supported, and their arm rested on the table at heart level. The nurse supervisor will then attach the Contec finger pulse oximeter to the participant's finger (opposite to the arm with the manual blood pressure cuff) and wait for a few seconds, to make sure a stable signal is received, and the device displays both the participant's pulse and SpO₂ values. Once the values are displayed, the nurse supervisor will hit the "Add session" button, and choose the correct device to connect to via Bluetooth. The calibration process will begin, indicated by the orange background, and the MediBeat application will display the participant's heartrate and SpO₂ values. It is critical that the participant does not move during the calibration process, which will last just over 1 minute. The background of the application will turn blue once calibration has completed successfully.

Recruitment plan

Inclusion/Exclusion Criteria

Healthy participants who are over the age of 25 and live or work in the North Simcoe Muskoka and Markham regions will be recruited to participate in this study. As outlined in the ESH-IP, only healthy subjects will be included this study; those who have heart arrhythmias, atrial fibrillations or atrial flutters, an inaudible Korotkoff sound, wounds of the upper arms/wrists, missing fingers, and/or an arm circumference of more than 55 cm will be excluded, in advance if at all possible, and at the study site if not previously excluded.

Recruitment will continue until the following quotas are met:

1. Numbers: At least 85 who fully complete the study protocol, and fall within the parameters listed in #3
2. Sex: At least 26 male and 26 female (each 30% of the total number of participants)

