3. Blood pressure range: 26 to 31 subjects in each of the three SBP and three DBP recruitment ranges as shown in Form 3 – Study Results (**Appendix N**):
 - Low blood pressure (systolic: 0-129, diastolic: 0-79)
 - Medium blood pressure (systolic: 130-160, diastolic: 80-100)
 - High blood pressure (systolic: 161 or higher, diastolic: 101 or higher).

Participant Remuneration

To thank participants for their valuable time, they will be provided with a \$50 VISA pre-paid gift card at the end of the study visit.

Recruitment Methods

Recruitment flyers (**Appendix E**) will also be posted in public spaces at corporate offices and medical clinics, who have agreed to participate within Central Ontario, including Markham, Toronto, and North Simcoe Muskoka.

Recruitment emails (**Appendix F**) will be sent to all relevant employees located at corporate offices and medical clinics, who have agreed to participate within Central Ontario, including Markham, Toronto, and North Simcoe Muskoka, with a link to [contact] to indicate interest. Recruitment will be a two-step process.

Clinical staff, from clinics who have agreed to participate, will be provided with a short script (**Appendix G**) and Frequently Asked Questions (FAQ) document (**Appendix H**) to assist with the recruitment process. Individuals interested in participating can submit a consent to contact form (**Appendix I**) to the clinic staff, who will scan and send the forms to the research team. **Research assistant** will call individuals who had expressed their interest in participating to further explain the study (**Appendix J**) and ask if they would like to participate. The research assistant will then inform them about the consent form (**Appendix K**) that they will be asked to sign at the study site. The research assistant will provide the participant with information about a scheduled time for participating in the study and directions.

Interactions with participants and Data collection

Form 1 - Device information

Prior to the first interaction with a participant, the supervisor will fill in the information about the device in Form 1 of the ESH-IP (**Appendix D**). As noted above, the Contec CMS50EW device is an electronic finger pulse oximeter (Contec Medical Systems Co., Ltd, Qianhuangdao, China) that generates a PPG, which is then sent to HeartBeat's proprietary algorithm to calculate blood pressure.

Confirmation of appropriate setting conditions

[figure not shown]

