- ☞ If possible, a permanent record of device measurements should be kept. If software is provided, device measurements should be downloaded daily.

Recruitment details

Date and time	201	Study number and Subject number	202	203
Date of birth	204	Age	205	
Sex	Male 206	On antihypertensive medication	Yes 207	No 207
Arm circumference cm	208	Cuff for test device	Standard 209	Other 209
Wrist circumference cm	210	Height ft, in		Weight lbs

Box 209: This is only required for arm devices. If the arm circumference is such that no suitable cuff is available, circle *Cuff size unavailable* in Box 287 and exclude the subject.

Box 210: This is only required for wrist devices.

Entry measurements

Ask the subject to relax for 10–15 min. Then make sure that the subject is seated with legs uncrossed and back supported. Ensure that the arm is supported at heart level. If a wrist device is being tested, the wrist must be supported according to the manufacturer's instructions. If the subject is not seated as described, the posture used must be recorded as a protocol adjustment.

BPA	Observer 1		Observer 2		Device		Heart Rate bpm	
	SBP	DBP	SBP	DBP	SBP	DBP		
	211	212		213	214		215	216
	Observer Mean			Category			Count	
BPA	SBP	DBP	SBP	DBP	SBP	DBP		
	217	218	LL L M H HH 219	LL L M H HH 220	221	222		

Boxes 217, 218: Enter the rounded up averages of Boxes 211 and 213 and of Boxes 212 and 214 respectively.

Box 219: Circle the range according to the BP in Box 217. LL: < 90, L: 90–129, M: 130–160, H: 161–180, HH: >180.

Box 220: Circle the range according to the BP in Box 218. LL: < 40, L: 40–79, M: 80–100, H: 101–130, HH: >130.

Boxes 221, 222: Update the running totals, for the ranges (counting LL and L together and counting HH and H together) in Boxes 219 and 220, and enter them respectively.

- ☞ If both Box 221 and Box 222 are greater than 12 or if an *LL* or *HH* is circled and there are already 4 such items circled, circle *Ranges complete* in Box 287 and exclude the subject.

- ☞ If one of Box 221 or Box 222 is greater than 12 but the other is not, it may be necessary to include this subject, and remove another, in order to achieve the correct range distribution; in the removed subject, circle *Range adjustment* in Box 287.

Validation measurements

	BP1		BP3		BP5		BP7	
	SBP	DBP	SBP	DBP	SBP	DBP	SBP	DBP
Observer 1	223	224	225	226	227	228	229	230
Observer 2	231	232	233	234	235	236	237	238
Observer mean	239	240	241	242	243	244	245	246

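### Form 2 keeps the 33-subject limit of 12 per blood pressure range, so followed literally it cannot deliver 85 subjects with 26 to 31 in each range

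*Combined protocol and SAP*

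**What the plan says.** **Target.** Section 3, Protocol, adopts the ESH-IP with a modification: the number of participants "should be at least 85 rather than 33". The Recruitment plan then says "Recruitment will continue until the following quotas are met" and lists:
- "At least 85 who fully complete the study protocol"
- "At least 26 male and 26 female"
- "26 to 31 subjects in each of the three SBP and three DBP recruitment ranges"

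Data Checking, item 4, repeats the 26 to 31 per range as a daily check. Appendix O gives the same figures for n = 85.

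**Form 2, Entry measurements.** Boxes 221 and 222 are the updated running totals for the subject's own SBP range and DBP range. The instruction "If both Box 221 and Box 222 are greater than 12" ends in exclusion as *Ranges complete*. The same sentence has a second, separate trigger for pressures in the extreme categories (LL or HH) once four have been used. If only one of the two totals is above 12, "it may be necessary to include this subject, and remove another", and the removed subject is marked *Range adjustment*.

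**Form 3.** The note to Boxes 314–323 asks for 10 to 12 subjects per range and exactly 33 in total. The notes that allow other totals or proportions (Boxes 312–323, Table 3, Table 5) are each worded for specific populations.

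**Standing of the form.** Of the clinicians, Health professionals involved says: "They will be instructed to follow the ESH-IP guidelines for data collection". The List of Appendices describes the subject data form as amended.

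**The concern.** The number 12 on Form 2 is the upper limit of the 33-subject design. The plan moved to 85 subjects and rescaled Appendix O, but not the form on which subjects are accepted or excluded at the study site. Two current instructions therefore give different stopping points for the same running totals: 12 on the form, and 26 to 31 in the Recruitment plan, Data Checking and Appendix O.

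Form 2 is used subject by subject, and its exclusion falls at the entry reading, after the person has attended and consented. If staff apply it as printed, eligible people are sent away to protect a range limit that no longer applies. Recruitment then cannot reach the quotas that are meant to end it.

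**Working it through.** **1. Where the 12 comes from.** Form 3 gives 10 to 12 per range for 33 subjects. Scaled to 85:
- 10 × 85/33 = 25.76, rounded to 26
- 12 × 85/33 = 30.91, rounded to 31

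This reproduces Appendix O's 26 to 31. The 12 on Form 2 is the unscaled counterpart of 31.

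**2. Ceiling under the 12-count rule.** A subject is admitted unless both updated totals exceed 12. So every admitted subject takes one of the first 12 places in the SBP range, in the DBP range, or in both.
- Places available: 6 ranges × 12 = 72.
- Among the first 12 admitted, no total can exceed 12, so each of them takes two places.
- Maximum admitted: 72 − 12 = 60.

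An exact search over all orders of arrival also gives 60.

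**3. The ceiling can be reached.** Number the ranges S1–S3 and D1–D3. Admit 12 subjects in each of (S1,D1), (S1,D2), (S1,D3), (S2,D1) and (S3,D1), in that order. All 60 pass the rule. The totals are then 36/12/12 for SBP and 36/12/12 for DBP, and every later subject is excluded.

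**4. Smallest range.** Suppose five ranges already exceed 12. The subject who would take the sixth to 13 has both totals above 12 and is excluded. At least one range therefore ends at 12 or fewer, at least 26 − 12 = 14 below the minimum.

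**5. Shortfall.** 85 − 60 = 25, so at least 25 of any 85 eligible subjects would be excluded.

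**6. Removals.** If removed subjects are subtracted from the totals, those who remain would also have been admissible, in the same order, had the removed subjects never been entered. So 60 is still the most that can be retained. If removals hold every range at 12, the number kept is at most 3 × 12 = 36.

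**7. Alternative reading of the boxes.** If the totals are compared with 12 before the current subject is added, the effective limit is 13. The ceiling is then 5 × 13 = 65 and the smallest range ends at 13 or fewer. The conclusion does not change.

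**8. Timing, 12-count trigger only.** No total can exceed 12 before the 13th eligible subject, so this trigger cannot exclude anyone earlier. With a ceiling of 60, it must have excluded someone by the 61st. The extreme-pressure trigger in the same sentence is separate and could act sooner.

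**9. Check of the remedy.** With the limit at 31, a split of 28 + 28 + 29 = 85 in SBP and in DBP is admissible. The *both totals* rule alone would allow 6 × 31 − 31 = 155 subjects, with one SBP and one DBP range at 155 − 2 × 31 = 93. It therefore does not hold ranges to 31. With every range held at 31, the maximum is 3 × 31 = 93.

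**The case against.** The strongest reply is that the intention is clear and would prevail. The Protocol section says the ESH-IP is modified to reach 85, the Recruitment plan continues until its quotas are met, and 26 to 31 per range is checked daily. The supervisor keeps the running totals on a separate sheet, and a familiarization session is planned. Staff may well work to 31, and a stop at 12 should surface quickly. This stands, and it limits the likely harm. It does not remove the contradiction: the form has no scaling clause, and the documents do not say which figure prevails.

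Form 3's flexibility notes might be thought to cover the point. The note to Boxes 314–323 allows other restrictions and totals and refers to Form 2, Boxes 219 and 220. But it is confined to specific populations, whereas this trial recruits healthy adults over 25, and the box reference may only name the data source.

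The 60 is also a bound. It needs a 36/12/12 split that itself breaks the quotas, so it should not be read as a forecast.

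Three stronger readings are tempting and are not supported:
- *The device would be judged against 33-subject pass marks.* Data Analysis ties the pass decision to Appendix O, which is scaled to 85 subjects and 255 pairs.
- *The exclusion list in Participant consent and interaction, item 14, contradicts the cap by omitting it.* That list matches Form 2's own Prerequisites list of events during the study, which also omits the cap because the cap belongs to the entry stage. The omission shows nothing either way.
- *No exclusion as Ranges complete can occur before the 13th subject.* That is true only of the 12-count trigger.

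**Conclusion.** The contradiction is real and should be corrected. Form 2's limit of 12 per range cannot coexist with at least 85 subjects and 26 to 31 per range. Applied literally, it retains at most 60 subjects (36 if every range is held at 12) and leaves at least one range 14 or more below its minimum. These bounds hold for any order of arrival and need no assumption about the mix of blood pressures. They assume only that the form is followed as printed, with the boxes including the current subject.

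A reader might infer that the trial will stop short of 85. The documents do not support that: the target is stated repeatedly and checked daily. The likely consequence is that eligible volunteers are turned away, and time is lost, until the conflict is seen. How many depends on what staff do in practice, which the documents do not show.

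**What to change.** In Form 2, Entry measurements, replace both limits of 12 with 31, the upper quota in Appendix O. State on the form that the Recruitment plan quotas and Appendix O govern recruitment counts. State also that the cap of 31 per range is kept through the existing *Range adjustment* step, since the *both totals* rule does not enforce it.

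As secondary clean-up in Form 3:
- replace 10–12 subjects per range with 26–31
- replace 22–44 readings per range with 57–113 (22 × 255/99 = 56.7; 44 × 255/99 = 113.3)
- replace the minimum of 10 per sex with 26
- replace the Table 5 marks with those in Appendix O
- change the total of exactly 33 to the number analysed (at least 85), and 99 readings to three times that number (255 for 85)

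Appendix O leaves the maximum difference of 19 and the limit of four out-of-range pressures at their 33-subject values. Whether that is intended is a separate question, and this edit should not be taken to settle it.

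The cost is an edit to two forms, with no added subjects, visits or time.

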2. Ensure the overall systolic blood pressure is within the range of ≤ 100 to ≥ 170 mmHg and the overall diastolic blood pressure is within the range of ≤ 50 to ≥ 120 mmHg.
3. If the participants have a blood pressure outside the range of 90–180mmHg for systolic blood pressure and 40–130mmHg for diastolic blood pressure, only a maximum of 4 blood pressures readings outside of this range can be included in the analysis.
4. Ensure there are approximately 26-31 participants in each of the 3 blood pressure ranges (low blood pressure (systolic: 0-129, diastolic: 0-79), medium blood pressure (systolic: 130-160, diastolic: 80-100) and high blood pressure (systolic: 161 or higher, diastolic: 101 or higher)).

Data Analysis

[figure not shown]
The profile of the study participants will be described based on a demographic analysis conducted on data collected from the subject data form from the ESH-IP (**Appendix M**).

All collected data on Forms 1 and 2 will be sent to the researchers at the SE Research Centre, who will consolidate the data from the Forms 1 and 2 and analyze the data as specified in Form 3, the Study Results form from the ESH-IP (**Appendix N**) (O'Brien et al., 2010).

In order to pass the validation process, the device must pass both parts 1 and 2 based on the accuracy criteria table (**Appendix O**).

Plots

These are mean-difference plots, and the plots modelled from the data collected should be exactly as shown in the example plots below.

The x-axis of these plots represents blood pressures in the systolic range 80mmHg–190mmHg and the diastolic range 30 mmHg–140 mmHg. The y-axes represent errors from – 30mmHg to +30mmHg. Horizontal reference lines will be drawn at 5mmHg intervals from +15mmHg to – 15 mmHg. The mean of each device pressure and its corresponding observer pressure will be plotted against their difference with a point. Differences greater than 30mmHg will be plotted at 30 mmHg. Differences less than – 30mmHg will be plotted at – 30 mmHg. The same scales will be used for both SBP and DBP plots. Where points are superimposed, these will be indicated either by proportionately larger points or by different symbols.

5. Confidentiality and security of data

Electronic data

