Observer difference	247	248	249	250	251	252	253	254
	BP2		BP4		BP6		Difference	
	SBP	DBP	SBP	DBP	SBP	DBP	A	0–5 mmHg
Device	255	256	257	258	259	260	B	6–10 mmHg
Device–Previous observer	261	262	263	264	265	266	C	11–15 mmHg
Device–Next observer	267	268	269	270	271	272	D	> 15 mmHg
Error group	A B C D 273	A B C D 274	A B C D 275	A B C D 276	A B C D 277	A B C D 278	Within 5 mmHg	
Observer value	281	282	283	284	285	286	SBP	DBP

Boxes 239–246: Enter the rounded up averages of Boxes 223 and 231, of Boxes 224 and 232, of Boxes 225 and 233, of Boxes 226 and 234, of Boxes 227 and 235, of Boxes 228 and 236, of Boxes 229 and 237 and of Boxes 230 and 238 respectively.

Boxes 247–254: Enter the differences Box 223–Box 231, Box 224–Box 232, Box 225–Box 233, Box 226–Box 234, Box 227–Box 235, Box 228–Box 236, Box 229–Box 237, and Box 230–Box 238 respectively.

Boxes 261–266: Enter the 'Device–Previous Observer Mean' differences. These are Box 255–Box 239, Box 256–Box 240, Box 257–Box 241, Box 258–Box 242, Box 259–Box 243, and Box 260–Box 244 respectively.

Boxes 267–272: Enter the 'Device–Next Observer Mean' differences. These are Box 255–Box 241, Box 256–Box 242, Box 257–Box 243, Box 258–Box 244, Box 259–Box 245, and Box 260–Box 246 respectively.

Each device measurement is compared to the nearer of the previous and next observer measurement. As described below, the smaller error is circled and the corresponding observer measurement is copied to aid the analysis.

Box 273: First, circle the smaller value, in absolute terms, of Boxes 261 and 267 (Box 261 if both are the same). Then circle A if this is less than or equal to 5, B if this is 6–10, C if this is 11–15 or D if this is greater than 15.

Boxes 274–278: Circle A, B, C or D, as described for Box 273, based on the smallest absolute values (also circled) of Boxes 261 and 268, Boxes 263 and 269, Boxes 264 and 270, Boxes 265 and 271 and Boxes 266 and 272 respectively.

Box 279: Enter the number of 'A's circled in Boxes 273, 275 and 277.

Box 280: Enter the number of 'A's circled in Boxes 274, 276 and 278.

The numbers of 'A's, 'B's and 'C's will be used in the analysis to calculate the number of device-observer differences within 5 mmHg, 10 mmHg and 15 mmHg.

Box 281: Enter the value in Box 239 if Box 261 is circled or Box 241 if Box 267 is circled.

Box 282: Enter the value in Box 240 if Box 262 is circled or Box 242 if Box 268 is circled.

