Boxes 357–358: Enter the mean and, in parentheses, the SD of the observer differences. Values should be rounded up to one decimal place e.g. 0.3 (1.2) (Boxes 247, 249, 251 and 253 and Boxes 248, 250, 252 and 254).

Boxes 359: Enter the number of measurements that were repeated in the included subjects because observers were more than 4 mmHg apart.

Table 5 Validation results

Part 1		$\leq 5\text{mmHg}$	$\leq 10\text{mmHg}$	$\leq 15\text{mmHg}$	Grade 1	Mean	SD
Pass requirement	Two of	73	87	96			
	All of	65	81	93			
Achieved	SBP	360	361	362	363	364	365
	DBP	366	367	368	369	370	371
Part 2		$2/3 \leq 5\text{mmHg}$	$0/3 \leq 5\text{mmHg}$	Grade 2	Grade 3		
Pass requirement		≥ 24	≤ 3				
Achieved	SBP	372	373	374	375		
	DBP	376	377	378	379		
Part 3		Result					
		380					

In order for the device to pass, all protocol requirements must be fulfilled. A fail in any part will result in an overall fail

Box 360: Enter the number of SBP differences (at most 99) between observer and device measurements falling within 5 mmHg.
(The total number of *Boxes* 273, 275 and 277 circled A in the 33 subjects)

Box 361: Enter the number of SBP differences (at most 99) between observer and device measurements falling within 10 mmHg.
(The total number of *Boxes* 273, 275 and 277 circled A or B in the 33 subjects)

Box 362: Enter the number of SBP differences (at most 99) between observer and device measurements falling within 15 mmHg.
(The total number of *Boxes* 273, 275 and 277 circled A, B or C in the 33 subjects)

Box 363: If Boxes 360, 361 and 362 fulfil the Pass requirements, then this is 'Pass'; otherwise, it is 'Fail'.

Boxes 364–365: Enter the mean and standard deviation respectively of the 99 SBP differences between observer and device measurements. (Use data from circled *Boxes* 261 or 267, 263 or 269 and 265 or 271)

Box 366: Enter the number of DBP differences (at most 99) between observer and device measurements falling within 5 mmHg.
(The total number of *Boxes* 274, 276 and 278 circled A in the 33 subjects)

Box 367: Enter the number of DBP differences (at most 99) between observer and device measurements falling within 10 mmHg.
(The total number of *Boxes* 274, 276 and 278 circled A or B in the 33 subjects)

Box 368: Enter the number of DBP differences (at most 99) between observer and device measurements falling within 15 mmHg.
(The total number of *Boxes* 274, 276 and 278 circled A, B or C in the 33 subjects)

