Box 369: If Boxes 366, 367 and 368 fulfil the Pass requirements, then this is 'Pass'; otherwise, it is 'Fail'.

Boxes 370–371: Enter the mean and standard deviation respectively of the 99 DBP differences between observer and device measurements. (Use data from circled *Boxes* 262 or 268, 264 or 270 and 266 or 272)

Box 372: Enter the number of subjects (at most 33) with two or three of the absolute differences between observer and device SBP measurements within 5 mmHg. (*Box* 279 is 2 or 3)

Box 373: Enter the number of subjects (at most 33) with none of the absolute differences between observer and device SBP measurements within 5 mmHg. (*Box* 279 is 0)

Box 374: If Boxes 372 and 373 fulfil the Pass requirements, then this is 'Pass'; otherwise, it is 'Fail'.

Box 375: If Boxes 363 and 374 are both 'Pass', then this is 'Pass'; otherwise, it is 'Fail'.

Box 376: Enter the number of subjects (at most 33) with two or three of the absolute differences between observer and device DBP measurements within 5 mmHg. (*Box* 280 is 2 or 3)

Box 377: Enter the number of subjects (at most 33) with none of the absolute differences between observer and device DBP measurements within 5 mmHg. (*Box* 280 is 0)

Box 378: If Boxes 376 and 377 fulfil the Pass requirements, then this is 'Pass'; otherwise, it is 'Fail'.

Box 379: If Boxes 369 and 378 are both 'Pass', then this is 'Pass'; otherwise, it is 'Fail'.

Box 380: If Boxes 375 and 379 are both 'Pass', then this is 'Pass'; otherwise, it is 'Fail'.

In validations carried out in specific populations requiring more than 33 subjects, proportionally equivalent passing criteria should be used.

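### The only planned mean and SD of device error come from differences selected for closeness, which generally shrinks the SD and pulls a non-zero bias toward zero

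*Combined protocol and SAP*

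**What the plan says.** Form 2 (Validation measurements) records two signed errors for each device reading: device minus previous observer mean (Boxes 261–266) and device minus next observer mean (Boxes 267–272). It then applies the rule that "Each device measurement is compared to the nearer of the previous and next observer measurement". The smaller error in absolute value is circled, a tie going to the previous reading, and the matching observer value is carried to Boxes 281–286.

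Form 3, Table 5 asks, for systolic pressure, "Enter the mean and standard deviation respectively of the 99 SBP differences between observer and device measurements", with the direction "Use data from circled *Boxes* 261 or 267, 263 or 269 and 265 or 271". For diastolic pressure the direction is "Use data from circled *Boxes* 262 or 268, 264 or 270 and 266 or 272". Both use circled values only.

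The protocol's Data Analysis section says the researchers will "analyze the data as specified in Form 3, the Study Results form from the ESH-IP". Under Plots it says: "The mean of each device pressure and its corresponding observer pressure will be plotted against their difference with a point". Form 2 uses the word 'corresponding' for the observer value that goes with the circled error, so the plots most naturally use the selected value too, although this is not spelled out.

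No other summary of device error is named. Boxes 357–358 compare the two observers with each other, and Boxes 343–344 describe recruitment pressures.

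**The concern.** The reference for each device reading is picked because it lies closer to that reading. For grading, this is a convention of the adopted ESH-IP. As an estimate of error it is selection on the outcome. Suppose a device reads 140 between observer means of 132 and 138: the errors are +8 and +2, the form keeps +2, and the error against the average of the two observer means is +5.

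The protocol's stated purpose is to validate the algorithm's accuracy, with applications to Health Canada and the FDA to follow if it is shown to be accurate. A reader of Table 5 would naturally take its mean and SD as the device's bias and spread. With no unselected figure beside them, that reader cannot tell how much of the apparent accuracy comes from the choice of reference.

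**Working it through.** **The plan's own figures.** The documents state no expected bias, SD or power, so there is no planned mean or SD to reproduce. What can be reproduced is the frame: 85 × 3 = 255 pairs, and the Form 3 thresholds scaled to Appendix O. For Part 1, 73, 87 and 96 times 255/99 give 188.03, 224.09 and 247.27; 65, 81 and 93 give 167.42, 208.64 and 239.55. For Part 2, 24 and 3 times 85/33 give 61.82 and 7.73. These round to the stated 188/224/247, 167/209/240, 62 and 8. None is a threshold for a mean or SD.

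**Inputs for the size (assumptions, not in the documents).** Device error X is normal with mean b and SD sx. The observer means before and after, o1 and o2, vary about the true pressure with SD so, which covers observer error and reading-to-reading change. At first o1 and o2 are independent and there is no trend.

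**Formulas.** e1 = X − o1 and e2 = X − o2.
- Average of both: (e1 + e2)/2, with mean b and SD √(sx² + so²/2).
- One pre-specified reading: e1, with mean b and SD √(sx² + so²).
- Form 2 rule: whichever of e1 and e2 is smaller in absolute value. This was simulated with at least 1,000,000 pairs per setting and values rounded to 1 mmHg.

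**Average reference by formula.**
- sx 5: √(25 + 4.5) = 5.43 (so 3) and √(25 + 8) = 5.74 (so 4).
- sx 8: √(64 + 4.5) = 8.28 and √(64 + 8) = 8.49.
- Rounding to 1 mmHg adds a little, giving the simulated column below.

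| sx | so | SD, nearer (b = 0) | SD, average (b = 0) | Mean, nearer (b = +4) | Mean, average (b = +4) |
|---|---|---|---|---|---|
| 5 | 3 | 4.4 | 5.4 | 3.1 | 4.0 |
| 5 | 4 | 4.5 | 5.8 | 2.8 | 4.0 |
| 8 | 3 | 7.1 | 8.3 | 3.4 | 4.0 |
| 8 | 4 | 7.0 | 8.5 | 3.2 | 4.0 |

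The SD columns are for zero bias. At b = +4 the nearer-rule SD is higher, about 4.7–4.85 (sx 5) and 7.2–7.3 (sx 8).

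**Wider grid** (b 0, 3, 5, 8; sx 5, 8, 10; so 2, 4, 6). The nearer-rule SD is 3% to 23% below the average-reference SD and 7% to 35% below the SD from one pre-specified reading. A non-zero bias shrinks by 8% to 40%. Recording observers to 2 mmHg and rounding their average up, as the forms direct, changes nothing material: at b 5, sx 8, so 4 the nearer rule gives 3.98 and 7.31, against 3.99 and 7.30 without rounding.

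**Where the effect weakens or reverses.**
- Correlated bracketing readings: at correlation 0.8, a bias of +4 is reported as about +3.5 to +3.7.
- Zero bias with symmetric errors: the mean stays at zero.
- Strong skew: with true mean 1.0 and median −1.4, the nearer-rule mean is 1.26, further from zero, while the SD still falls (7.20 against 8.94 for one pre-specified reading).
- Dominating bias: at b 15, sx 3, so 4, the nearer-rule SD is 4.46 against 4.13 for the average reference. The mean is still pulled down, to 12.74.

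**The case against.** The strongest reply is that the rule belongs to the ESH-IP, which the protocol undertakes to follow. Form 3 openly says that circled boxes are used, both unselected differences remain on Form 2, and passing rests on the Part 1 and Part 2 counts. All of that stands. This is a limitation of the adopted method and not a departure from it, and no pass or fail decision turns on the mean or SD. The reply does not answer the reporting gap: data that stay on Form 2 unsummarised do not reach a reader of Table 5.

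A second reply is that the average of both readings does not recover the device's own SD. That also stands. With device SD 5 and observer SD 4, the nearer rule gives about 4.5 (0.5 low) and the average about 5.75 (0.75 high). The average removes the bias shrinkage and the selection, but its SD carries observer and reading-to-reading variability, and the report should say so.

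A reader might infer that the reported SD must fall below the device's own error SD. It need not. With device SD 5 it is 5.07 at observer SD 6 and no bias, and 5.04–5.30 at bias +4 with observer SD 3–4 and correlation 0.5. Correlation is plausible, since Form 2 allows only 30 to 60 seconds between measurements.

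Finally, the 2018 consensus statement (Appendix B) is said to modify the protocol and is not reproduced here. It might call for a further summary, but the Data Analysis section names only Form 3.

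**Conclusion.** The point holds as a reporting weakness. The only planned mean and SD of device error rest on differences selected after the device value is known, and relative to an unselected reference this generally lowers the SD and draws a non-zero bias toward zero. Under the stated assumptions, roughly 15% to 30% of a +4 mmHg bias disappears (0.6/4 to 1.2/4). The zero-bias SD is about 14% to 22% below the average-reference SD (for example 1 − 7.1/8.3 and 1 − 4.5/5.8). These sizes depend on SDs, independence and symmetry that the documents do not supply.

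Two stronger readings are not supported. One is that the understatement is guaranteed: skewed errors, a dominating bias and correlated readings show that it is a tendency. The other is that the validation result is thereby invalid: neither Table 5 nor Appendix O sets a threshold for the mean or SD, and the grading counts apply the adopted protocol's own rule.

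**What to change.** Leave the ESH-IP grading rule as it is. Before analysis begins, specify the following:

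- Add to Table 5, for SBP and DBP separately, the mean and SD of device minus the average of the previous and next observer means. For the first systolic reading this is Box 255 − (Box 239 + Box 241)/2, and likewise for the others.
- Add a mean-difference plot for each pressure drawn from these differences.
- Present these as the accuracy estimate, and state that the SD includes observer and reading-to-reading variability.
- Label Boxes 364–365 and 370–371 'nearer-reference', and state which observer value the existing plots use.
- While editing, reconcile the instruction for Boxes 274–278, which pairs Box 261 with Box 268 (systolic with diastolic), with Box 282 and Boxes 370–371, which use 262 or 268. Update the references to 99 differences to match the 255 pairs in Appendix O.

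The cost is four extra numbers and one extra pair of plots from data already on Form 2, with no new measurements. The drawback for the sponsor is a usually less favourable reported SD.
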